11.3.2 Analysis of Secondary Endpoints

With adequate follow-up time, secondary endpoints of progression-free survival (PFS) and overall survival (OS) will be assessed by Kaplan-Meier survival analysis and 95% confidence intervals for median PFS/OS will be calculated using Greenwood's formula. PFS will be defined as the time from first treatment day until objective or symptomatic progression. OS will be defined as the time from first treatment day until death. The frequency of subjects experiencing toxicities will be tabulated. Toxicities will be assessed and graded according to CTCAE v. 4.0 terminology. Exact 95% confidence intervals around the toxicity proportions will be calculated to assess the precision of the obtained estimates.

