1.2 Secondary Objectives

The secondary objectives of the study are: 1) to estimate the median progression free survival and the median overall survival for patients treated with immunotherapy and radiotherapy, and 2) to assess the toxicity (per CTCAE version 4.0) of patients treated with immunotherapy and radiotherapy.

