5.1.2 Treatment Phase

Once eligible, patients will receive immunotherapy, nivolumab, intravenously at 240 mg every two weeks. Infusions will be given over 30 minutes (not bolus or IV push). Patients will also receive radiation of 6 Gy x 5 fractions the first week of starting immunotherapy. Immunotherapy treatment starts with the first radiotherapy fraction. Nivolumab will be given every 2 weeks. Patients will have specified laboratory values measured monthly and evaluated for response as defined by International Myeloma Working Group Criteria. Patients will continue to receive their respective immunotherapy for up to three years or until disease progression or dose limiting toxicity is reached. Patients will remain on therapy for up to 6 cycles in the setting of stable disease and for up to a year in the setting of a PR or better by 6 cycles.

5.2 Response Assessment at Week 12

Patients will have specified laboratory values measured monthly and evaluated for response as defined by International Myeloma Working Group Criteria. Patients without progression of disease as defined by IMWG criteria including assessment of plasmacytoma(s) by PET/CT will continue to receive nivolumab every 2 weeks.

5.3 Duration of Therapy and Criteria for Removal from Study:

In the absence of treatment delays due to adverse event(s), treatment may continue until one of the following criteria applies:

1. Progression of disease as defined by IMWG criteria,
2. Intercurrent illness that prevents further administration of treatment,
3. Unacceptable adverse event(s),
4. Patient decides to withdraw from the study, or
5. General or specific changes in the patient's condition render the patient unacceptable for further treatment in the judgment of the investigator.

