5.4 Duration of Follow Up

Patients will be followed for 3 years after removal from study or until death, whichever occurs first. Patients removed from treatment for unacceptable adverse events will be followed until resolution or stabilization of the adverse event

6 Radiation Therapy Guidelines

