Progressive disease ^{††,Ω}	
Any one or more of the following criteria:
 
Increase of 25% from lowest confirmed response value in one or more of the following criteria:
 
 Serum M-protein (absolute increase must be ≥ 0.5 g/dL); Serum M-protein increase ≥ 1 g/dL, if the lowest M component was ≥ 5 g/dL; Urine M-protein (absolute increase must be ≥ 200 mg/24 h); 
In patients without measurable serum and urine M-protein levels, the difference between involved and uninvolved FLC levels (absolute increase must be > 10 mg/dL);
 
In patients without measurable serum and urine M-protein levels and without measurable involved FLC levels, bone marrow plasma-cell percentage irrespective of baseline status (absolute increase must be $\geq 10\%$); Appearance of a new lesion(s), $\geq 50\%$ increase from nadir in SPD^{§§} of > 1 lesion, or $\geq 50\%$ increase in the longest diameter of a previous lesion > 1 cm in short axis;
 
$\geq 50\%$ increase in circulating plasma cells (minimum of 200 cells per μL) if this is the only measure of disease

Clinical relapse	
Clinical relapse requires one or more of the following criteria: Direct indicators of increasing disease and/or end organ dysfunction (CRAB features) related to the underlying clonal plasma-cell proliferative disorder. It is not used in calculation of time to progression or progression-free survival but is listed as something that can be reported optionally or for use in clinical practice; Development of new soft tissue plasmacytomas or bone lesions (osteoporotic fractures do not constitute progression);
 
Definite increase in the size of existing plasmacytomas or bone lesions. A definite increase is defined as a 50% (and ≥ 1 cm) increase as measured serially by the SPD^{§§} of the measurable lesion;
 
Hypercalcaemia (> 11 mg/dL);
 
Decrease in haemoglobin of ≥ 2 g/dL not related to therapy or other non-myeloma-related conditions; Rise in serum creatinine by 2 mg/dL or more from the start of the therapy and attributable to myeloma;
 
Hyperviscosity related to serum paraprotein

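### PFS is defined without death as an event and with an undefined symptomatic progression, so the secondary median would not be a PFS median

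*Combined protocol and SAP*

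**What the plan says.** Section 1.2 sets a secondary objective: "to estimate the median progression free survival and the median overall survival for patients treated with immunotherapy and radiotherapy". The only definition of PFS is in section 11.3.2: "PFS will be defined as the time from first treatment day until objective or symptomatic progression". The next sentence there brings in death, but only for the other endpoint: "OS will be defined as the time from first treatment day until death". Both endpoints "will be assessed by Kaplan-Meier survival analysis and 95% confidence intervals for median PFS/OS will be calculated using Greenwood's formula". No censoring rule is given, and nothing says how a death before progression is handled.

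Elsewhere, progression means IMWG progression. Section 5.2 continues treatment in patients without "progression of disease as defined by IMWG criteria", and section 5.3 uses the same standard as its first criterion for ending treatment. Section 9.1 lists the laboratory, marrow and lesion criteria for progressive disease. It lists clinical relapse as a separate category and says of it: "It is not used in calculation of time to progression or progression-free survival but is listed as something that can be reported optionally".

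**The concern.** Progression-free survival ends at progression or death. An endpoint that ends at progression alone is time to progression, and its median answers a different question. Under the written definition, a patient who died of toxicity before progressing would not count as a PFS failure. Such deaths are not remote: section 11.3.5 counts treatment-related death as a DLT, and section 2.4 describes excess deaths with a same-class drug in a combination not used here.

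The second half of the event list has a different problem. Symptomatic progression appears once and is never defined, so two analysts could date the event differently for the same patient. If it means clinical relapse, section 11.3.2 counts what section 9.1 excludes.

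At stake is a named secondary result that readers would set beside PFS medians from other studies.

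**Working it through.** **No figure to reproduce.** The plan states no PFS median, event count or precision. The check is of the text, followed by an illustration of size.

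**Text, side by side.**

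| Place | Progression | Death |
|---|---|---|
| 1.2 | PFS named, not defined | not mentioned for PFS |
| 5.2, 5.3 | IMWG criteria | not mentioned |
| 9.1 | IMWG progressive disease; clinical relapse kept out of PFS | not mentioned |
| 11.3.2, PFS | objective or symptomatic | absent |
| 11.3.2, OS | not applicable | the event |

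A Kaplan-Meier analysis has two states, event or censored. With death off the event list, a death without progression is censored. If it is censored on its own date, the curve cannot fall below the true PFS curve, so this departure alone leaves the median unchanged or longer.

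Counting clinical relapse would act the other way. Its lesion items overlap with progressive disease. Only hypercalcaemia, haemoglobin fall, creatinine rise or hyperviscosity without IMWG progression would add events.

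**Illustration of size.** Assumptions, none from the documents: constant, independent hazards p (IMWG progression), d (death without progression) and m (symptomatic event only).

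- f = d/(p+d), the share of true PFS events that are deaths without progression; assumed 10% to 30%.
- s = m/(p+m), the share of as-written events that are symptomatic only; assumed 5% to 20%.
- As-written median ÷ PFS median = (p+d)/(p+m) = (1−s)/(1−f).

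Death omitted only (s = 0), with 26 patients (the evaluable target in section 11.1) all followed to an event:

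| f | Ratio 1/(1−f) | Deaths censored, 26f | Events left |
|---|---|---|---|
| 10% | 1.11 | 2.6 | 23.4 |
| 20% | 1.25 | 5.2 | 20.8 |
| 30% | 1.43 | 7.8 | 18.2 |

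For an assumed true median of 4 months this gives 4/0.9 = 4.4, 4/0.8 = 5.0 and 4/0.7 = 5.7 months. A simulation of 26 patients cut off at 36 months gave typical medians of about 3.8 months with deaths counted, against 4.3, 5.0 and 5.7 with deaths censored.

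Symptomatic-only events counted (f = 0): 1−s = 0.95, 0.90 and 0.80 at s = 5%, 10% and 20%.

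Both departures:

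- lowest: (1−0.20)/(1−0.10) = 0.89
- highest: (1−0.05)/(1−0.30) = 1.36

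**Sampling error for comparison.** For n uncensored exponential times, SE(log median) = 1/(ln 2 × √n).

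- n = 26: 1/(0.693 × 5.099) = 0.283; exp(±1.96 × 0.283) = 0.57 to 1.74
- n = 30 (maximum accrual): 0.263; 0.60 to 1.68
- n = 13 (stop after stage one): 0.400; 0.46 to 2.19

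Simulation at n = 26 gave an SD of the log median of 0.278 and a 2.5% to 97.5% range of 0.55 to 1.65. With deaths censored at f = 30%, the range around the as-written median's own centre was 0.53 to 1.82, so censoring deaths also widens the sampling error. Every ratio above lies inside these ranges.

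**The case against.** The strongest reply is that the endpoint is called progression-free survival throughout, so an analyst would count deaths whatever the sentence says, and censoring of deaths is inferred, not written. A drafting slip is quite possible. But section 11.3.2 gives an explicit event list, and an analysis that follows it censors these deaths. Whether the result is right should not depend on the analyst departing from the plan.

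The conflict with section 9.1 rests on reading symptomatic progression as clinical relapse. That is an inference; the phrase could mean IMWG progression that presents with symptoms. So the conflict is possible, not proved. That the term is undefined holds on either reading.

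The size is also open. All shares are assumed, the net sign is unknown, section 11.3.2 names no PFS population, and the ratios lie within sampling error. If nobody dies before progression, the death omission changes nothing numerically. All of this stands and limits the weight of the point, but the confidence interval would still surround the wrong quantity.

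Finally, the calendar in section 5.1 ends at the end-of-study visit, and section 5.1.2 limits treatment in stable disease to 6 cycles. A death long after the last assessment could therefore count as a PFS event with no intervening search for progression. This is a fair caution about the censoring rule, not a reason to leave death out.

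**Conclusion.** The concern holds. As written, the endpoint is time to progression with an unclear symptomatic component, and its median would carry the PFS label. The omission of death is certain from the text; the clash with section 9.1 depends on what symptomatic progression was meant to cover.

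Over the assumed shares the as-written median is 1.11 to 1.43 times the PFS median from the death omission alone, 0.80 to 0.95 times from symptomatic-only events alone, and 0.89 to 1.36 times with both. These figures rest on constant, independent hazards and on shares the documents do not supply.

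The effect is confined to a descriptive secondary median in a single-arm trial. The primary response rule, OS, the DLT rule and SAE reporting are untouched. It should be corrected before the analysis, so that the event list is not chosen after the data are seen.

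**What to change.** Replace the PFS sentence in section 11.3.2 with, for example: PFS is the time from first treatment day to the first of progressive disease by the IMWG criteria in section 9.1 or death from any cause; patients without an event are censored at their last disease assessment. Delete symptomatic progression from the definition and report clinical relapse separately, which section 9.1 allows as an option. It would help to state also how a death after a long gap in assessment, or the start of another anti-cancer therapy, is treated; those rules are for the trial team to choose.

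If death was left out on purpose, rename the endpoint time to progression, reword the PFS objective in the protocol summary and section 1.2, and reconcile the symptomatic component with section 9.1.

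The cost is essentially one sentence. Section 5.4 already provides the deaths: "Patients will be followed for 3 years after removal from study or until death, whichever occurs first". Adding death as an event needs no new data. The drawback is that the reported median may be shorter.

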11.3.3 Interim Analysis

None Planned.

11.3.4 Reporting and Exclusions

11.3.5 Evaluation of toxicity

All patients will be evaluable for toxicity from the time of their first treatment with Investigational agent. A DLT will be defined as any grade 4 non-hematological toxicity or any toxicity that interrupts treatment for more than 6 weeks, treatment-related deaths, or grade 3 treatment-related non-hematological toxicities. Once 8 patients have been enrolled, we will use a continuous Bayesian toxicity stopping rule that will pause the study for review if the posterior probability that the DLT event rate is greater than 20% is $> 80\%$, using an uninformative prior of Beta(1,1). The trial will reviewed if 3 or more of the first 8 patients experience DLTs, or 4 or more of the first 9-12, or 5 or more of the first 13-16, 6 or more of the first 17-21, 7 or more of the first 22-25.

11.3.6 Evaluation of response.

All patients included in the study will be assessed for response to treatment if they have received at least 1 nivolumab infusion.

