1. Changing personnel : Replacing Research Nurse [name] with [name]
2. Changing personnel: Data Manager (Myeloma team): [name]
3. Section 3.3 - Exclusion criteria #12 - Prior exposure to immune checkpoint inhibitor
4. Correcting Nivolumab infusion from 60 mintues to 30 minutes as per BMS and FDA treatment prescriptions.
5. Clarifying stool collection timepoints : Baseline, end of radiation, C4D1 and C7D1
6. saliva collection added to the calendar for C1D1 (before infusion)
7. Adding investigator : [name]
8. Updated Appendix 2 : for stool collection timepoints.
9. Clarifying radiation given as 5 fractions and removing “consecutive days” language.
10. Removing immune monitoring blood samples from section 8.1, 14.2 and 14.5.
11. Revising bone marrow aspiration to 20ml.

Informed consent changes :

1. Clarifying that patients will receive 5 fractions of radiation treatment.

Protocol Summary

Full Title:	Radiotherapy and Immunotherapy for Systemic Effect in Myeloma (RISE-M) Trial
Short Title:	RISE-M Trial
Clinical Phase:	II
Principal Investigator:	[name], MD
Sample Size:	N = 30
Accrual Ceiling:	This study will enroll 30 subjects and screen up to 50.
Study Population:	Eligible patients will have multiple myeloma.
Accrual Period:	2 years
Study Design:	Eligible patients have multiple myeloma with measurable disease in the blood and a targetable soft tissue or bony lesion with radiotherapy. All eligible patients will receive immunotherapy (Nivolumab) plus radiotherapy, 6 Gy x 5 fractions, to a targetable lesion. Immunotherapy treatment starts with the first radiotherapy fraction. Nivolumab will be given every 2 weeks. Patients will have specified laboratory values measured bi-monthly and evaluated for response at 12 weeks as defined by International Myeloma Working Group Criteria. Patients will continue to receive their respective immunotherapy until disease progression or dose limiting toxicity is reached.
Study Duration:	Patients will have approximately 25-30 visits and a follow up for up to 3 years.
Study Agent/Intervention:	Patients with multiple myeloma will receive Nivolumab intravenously at 240 mg every two weeks. Infusions will be given over 30 minutes (not bolus or IV push). Patients will continue to receive infusions every two weeks until disease progression or dose limiting toxicity is reached. Patients will receive 5 fractions of radiation. A dose of 6 Gy x 5 days will be administered.

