13.2 Data and Safety Monitoring Plan (DSMP)

Study monitoring

There will be monthly reports generated for study accrual, observed AEs, and data timeliness. The study team will review these reports. In addition, the study will undergo periodic review by the Weill Cornell data safety and monitoring board (DSMB).

DSMB Safety Review

The protocol will be reviewed by the Data Safety Monitoring Board (DSMB) on a semi-annual basis. Safety reports will be submitted to the DSMB every six months.

ADMINISTRATIVE SECTION

Compliance with the Protocol and Protocol Revisions

The study will be conducted as described in the final approved protocol. Documentation of approval signed by the chairperson or designee of the IRB(s) will be sent to the WCM protocol manager.

All revisions (protocol amendments, administrative letters, and changes to the informed consent) will be submitted to the WCM protocol manager. The Investigator will not implement any deviation or change to the protocol without prior review and documented approval/favorable opinion from the IRB of an Amendment, except where necessary to eliminate an immediate hazard(s) to study

patients.

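### The DLT pause rule waits for the eighth enrolment even when a third DLT in patients 3 to 7 has already made the pause certain

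*Combined protocol and SAP*

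**What the plan says.** Section 11.3.5 sets a Beta(1,1) prior on the DLT rate. The study is paused for review when the posterior probability that this rate exceeds 20% is above 80%. The start is gated: "Once 8 patients have been enrolled, we will use a continuous Bayesian toxicity stopping rule". The section then lists boundaries, the first being "3 or more of the first 8 patients experience DLTs", followed by 4 at 9–12 patients, 5 at 13–16, 6 at 17–21 and 7 at 22–25. No number is given for fewer than 8 patients, and no DLT observation window is stated.

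The DLT definition in the same section includes any toxicity that interrupts treatment for more than 6 weeks.

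Other safety oversight is in sections 12.2 and 13.2. SAEs go to the institution and the drug supplier within 24 hours, and to the IRB and DSMB. The study team reviews monthly AE reports. For the board, "Safety reports will be submitted to the DSMB every six months". Section 12.2 also mentions an annual committee review. None of these carries a numeric trigger or requires accrual to pause.

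The Protocol Summary gives the planned size, "This study will enroll 30 subjects and screen up to 50", and a 2-year accrual period.

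**The concern.** The rule is described as continuous, yet it is off until the eighth enrolment. The gap matters in one situation: three of the first 3 to 7 patients have a DLT. The boundary at 8 must then be crossed whatever happens next. As written, though, the site goes on enrolling until there are 8 patients, and only then pauses. Those additional patients are exposed to a regimen that the plan's own criterion already marks for review.

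At the planned pace of 30 patients in 24 months (1.25 per month), 8 enrolments take 8 / 1.25 = 6.4 months. That is about one DSMB reporting interval, so the periodic reviews may not close the gap.

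**Working it through.** **Inputs**, all from section 11.3.5: prior Beta(1,1); target DLT rate 20%; cut-off 80%; start at 8 enrolled; first boundary 3 of 8; later boundaries as printed.

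**1. Reproduce the first boundary.** With x DLTs in n patients the posterior is Beta(1+x, 1+n−x), and Pr(rate > 0.20) = Pr(Bin(n+1, 0.20) ≤ x).
- 3 of 8: 0.914, above 0.80.
- 2 of 8: 0.738, below 0.80.

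So 3 of 8 is the correct first boundary under the stated criterion.

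**2. Apply the same criterion to 3 DLTs before patient 8.** For 3 of 3 the posterior is Beta(4,1), giving 1 − 0.2⁴ = 0.998. The others are 0.993 (3 of 4), 0.983 (3 of 5), 0.967 (3 of 6) and 0.944 (3 of 7). All exceed 0.80, and none can lead to fewer than 3 of 8.

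**3. How often, and how many patients.** Assume independent patients with DLT rate p, and each DLT known before the next enrolment. The third DLT falls at patient k with probability C(k−1, 2) p³ (1−p)^(k−3), and 8−k patients then follow before the pause.

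For p = 0.40 and k = 3 to 7 the probabilities are 0.0640, 0.1152, 0.1382, 0.1382 and 0.1244, which sum to 0.580. Weighted by 5, 4, 3, 2 and 1 they give 1.60 patients, and 1.60 / 0.580 = 2.75.

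| True DLT rate | P(third DLT by patient 7) | Mean further patients, given this | Mean further patients, all trials |
|---|---|---|---|
| 20% | 0.148 | 2.3 | 0.34 |
| 30% | 0.353 | 2.5 | 0.88 |
| 40% | 0.580 | 2.8 | 1.60 |
| 50% | 0.773 | 3.1 | 2.37 |

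**4. Effect on the overall pause probability.** Every sequence with 3 DLTs by patient 7 also has at least 3 by patient 8, so acting at the third DLT pauses exactly the same trials, only earlier. An exact recursion over the printed boundaries to patient 25 gives the same pause probability with and without early action: 0.057, 0.376, 0.769, 0.956 and 0.996 at DLT rates of 10%, 20%, 30%, 40% and 50%. Expected patients enrolled at the pause (or 25 if none) fall from 20.06 to 19.72 at 20%, 14.51 to 13.63 at 30%, 10.63 to 9.03 at 40%, and 8.83 to 6.47 at 50%. The equality does not depend on the later boundaries. Several of those do not follow from the stated criterion (3 of 9 already gives 0.879, but 4 are required), which is a separate matter.

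**5. Late recognition.** Six weeks is about 1.4 months, and 1.4 × 1.25 is about 1.7 enrolments. If two more patients are enrolled before the third DLT is recognised, the saving is the mean of max(8−k−2, 0): 0.09, 0.27, 0.56 and 0.94 patients at 20%, 30%, 40% and 50%.

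**6. Why a gate exists.** Under Beta(1,1) the 80% criterion is crossed by 1 DLT in 1, 2 or 3 patients (0.960, 0.896, 0.819) and by 2 in 4, 5 or 6 (0.942, 0.901, 0.852). Run from the first patient, it would pause by patient 7 with probability 0.29 at a DLT rate of 10% and 0.54 at 20%.

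**The case against.** The strongest defence is that a minimum sample size is sound practice. Step 6 supports it: without the gate, a single early DLT would pause a trial whose true rate is 10%. That stands, and the gate on the posterior criterion should remain. It does not justify waiting after a third DLT, where the decision is already fixed.

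It can also be said that 3 of the first 8 is met as soon as the third DLT occurs. That reading is possible, but the gating sentence points the other way. If early action is intended, the text should say so.

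Third, crossing the boundary leads to a review, not termination, and the gain is modest: less than one patient on average at DLT rates up to 30%, and less again if DLTs are recognised late. This stands and limits the weight of the point.

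A reader might also infer more than the documents support:
- That the extra patients are treated for no information. Section 11.3.6 assesses response in everyone with at least one infusion, and their DLT data inform the review (the posterior is 0.993 at 3 of 4 and 0.914 at 3 of 8). What they cannot inform is whether to pause.
- That patients 1 to 7 are unwatched. The monthly AE review, SAE reporting and DSMB reports cover them. What is missing is a numeric trigger.
- That this is the first use of the regimen, or that it carries a known excess-death signal. The documents call the study a pilot but do not say first use. The signal in section 2.4 concerns pembrolizumab with dexamethasone and an immunomodulatory agent, neither of which is given here; the same section reports acceptable drug-related adverse events in a nivolumab study that included 26 myeloma patients.

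**Conclusion.** The point holds as a gap in the wording of the pause rule. Once a third DLT has occurred in patients 3 to 7, the literal text allows 1 to 5 further enrolments that cannot alter the pause decision. The certainty of the pause follows from the boundary alone and needs no assumption. The sizes in step 3 assume independent patients and immediate knowledge of each DLT, so they are upper figures; step 5 shows how far a two-patient delay reduces them. Nothing here implies that the gate lowers the chance of detecting excess toxicity: the overall pause probability is identical either way. The correction is worth making because it is simple and the potential exposure is avoidable.

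**What to change.** In section 11.3.5, keep the gate at 8 enrolled patients on the posterior-probability criterion and leave the listed boundaries as they are. Add a separate sentence, for example: *In addition, while fewer than 8 patients are enrolled, accrual is paused for the same review as soon as a third patient has had a DLT.*

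The early trigger must be an addition. Deleting the gate would leave the posterior criterion with no stated start and open the way to the early pauses in step 6.

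The cost is one sentence, with no extra patients, no new analysis and no added probability of a pause. The small downside is that a review brought forward in this way has data from 3 to 7 patients rather than 8.

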11.1 Sample Size/Accrual Rate

As mentioned, a Simon's two-stage optimal design [Simon, 1989] will be used. The null hypothesis that the true response rate is 20% will be tested against a one-sided alternative. If there are 3 or fewer responses in these 13 patients, the study will be stopped. Otherwise 13 additional patients will be accrued for a total of 26 patients. The null hypothesis will be rejected if 10 or more responses are observed in 26 patients. This design yields a one-sided type I error of 0.025 and power of 60% when the true response rate is 40%. The target sample size is 26 evaluable patients and up to 30 patients (4 extra patients) will be accrued to account for non-evaluable patients or patients who withdraw prior to evaluation.

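### The printed DLT review counts do not follow the stated Bayesian rule: they are one DLT higher at 9 of 18 sample sizes, and the list ends at 25 of up to 30 patients

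*Combined protocol and SAP*

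**What the plan says.** Section 11.3.5 (Evaluation of toxicity) first states the rule in words: "Once 8 patients have been enrolled, we will use a continuous Bayesian toxicity stopping rule". The study pauses for review if the posterior probability that the DLT rate is above 20% exceeds 80%, with a Beta(1,1) prior. The next sentence turns this into counts: "The trial will reviewed if 3 or more of the first 8 patients experience DLTs, or 4 or more of the first 9-12". The printed threshold then rises to 5 DLTs for patients 13 to 16, to 6 for patients 17 to 21 and to 7 for patients 22 to 25. The list ends there.

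The same section sets the population: "All patients will be evaluable for toxicity from the time of their first treatment with Investigational agent". Section 11.1 targets 26 evaluable patients and adds that "up to 30 patients (4 extra patients) will be accrued" to allow for non-evaluable patients and withdrawals. Toxicity monitoring can therefore run to 30 patients.

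**The concern.** The prior, the DLT-rate threshold and the probability cut-off are all given, so each sample size has exactly one boundary. The printed bands are too short at the start: under a flat prior, 3 DLTs remain strong evidence against a 20% rate beyond the eighth patient, but the list moves to 4 at the ninth.

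This is the only quantitative safety trigger at study level. Section 11.3.3 plans no interim analysis, and Table 1 in section 7.4 governs individual patients. If the study team and the DSMB work from the counts, the study will continue in situations where the preceding sentence calls for a pause. If they work from the posterior, they will contradict the printed list. The choice would then be made mid-trial, with a DLT signal already in hand.

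**Working it through.** **Inputs.** From section 11.3.5: prior Beta(1,1), DLT-rate threshold 0.20, cut-off above 0.80, first look at n = 8, and the printed counts. From section 11.1: up to 30 patients.

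**Formula.** With k DLTs in n patients the posterior is Beta(1 + k, 1 + n − k). For this prior,

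Pr(rate > 0.20 | k, n) = Pr(X ≤ k), where X ~ Binomial(n + 1, 0.20).

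The boundary at n is the smallest k for which this exceeds 0.80.

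**The plan's own figure at n = 8.** 2/8 gives 0.738 and 3/8 gives 0.914, so the boundary is 3. The printed count is reproduced.

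**At n = 9.** For k = 3, X ~ Binomial(10, 0.20): 0.1074 + 0.2684 + 0.3020 + 0.2013 = 0.879. This is above 0.80, so the boundary is still 3. The list prints 4.

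**All sample sizes.**

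| DLTs needed | Stated rule, n | Printed list, n |
|---|---|---|
| 3 | 8-10 | 8 |
| 4 | 11-14 | 9-12 |
| 5 | 15-19 | 13-16 |
| 6 | 20-23 | 17-21 |
| 7 | 24-27 | 22-25 |
| 8 | 28-30 | none |

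The two agree at n = 8, 11, 12, 15, 16, 20, 21, 24 and 25 (9 of 18). At the other nine the printed count is exactly one higher. The posterior probability one DLT below the printed count is then already above 0.80:

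| DLTs / n | Posterior probability |
|---|---|
| 3/9 | 0.879 |
| 3/10 | 0.839 |
| 4/13 | 0.870 |
| 4/14 | 0.836 |
| 5/17 | 0.867 |
| 5/18 | 0.837 |
| 5/19 | 0.804 |
| 6/22 | 0.840 |
| 6/23 | 0.811 |

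**Could another cut-off explain the list?** Not with Beta(1,1) and 20%. The list does not trigger at 3/9 (0.879) but does trigger at 6/21 (0.867). A single cut-off cannot pass over the larger value and act on the smaller.

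**Could another prior?** Yes. Of the variants tried, two reproduce all 18 printed counts at the 20% threshold: a near-improper Beta(0.001, 0.001) prior with the 80% cut-off, and Beta(2, 8) with a 75% cut-off. The documents state neither. The two also disagree beyond the list: at n = 30 the first gives 9 and the second gives 8. The printed counts alone therefore do not determine how to extend the list.

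**Effect on the chance of a review.** Exact recursion, looking after every patient from n = 8, with independent DLTs at a constant rate:

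| True DLT rate | Printed list, to n = 25 | Stated rule, to n = 25 | Stated rule, to n = 26 | Stated rule, to n = 30 |
|---|---|---|---|---|
| 10% | 5.7% | 9.4% | 9.4% | 9.5% |
| 20% | 37.6% | 47.6% | 48.3% | 50.0% |
| 25% | 58.9% | 68.0% | 69.0% | 71.4% |
| 30% | 76.9% | 83.3% | 84.2% | 86.4% |
| 40% | 95.6% | 97.2% | 97.5% | 98.3% |

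The first two columns of probabilities share a horizon and isolate the effect of the wrong counts. The last two add the looks for which no count is printed.

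**The case against.** The arithmetic is not in dispute. The case on the other side concerns weight and direction.

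- *The list may be the intended half.* It is coherent under a different prior or cut-off, so the mistake could lie in the stated prior. This stands: the documents do not show which half was meant, and the fix has to allow for both. It does not remove the contradiction.
- *The gap is modest on a common horizon.* To n = 25 the difference is 10.0 percentage points at a true rate of 20%, 6.4 at 30% and 1.6 at 40%. This also stands, and these are the figures to use for the effect of the counts alone.
- *Patients 26 to 30 are not without a rule.* The rule in words is continuous and has no upper limit, so a boundary can be computed there. That is right; only the printed list stops. The range is also reached only if at least 4 of the first 13 evaluable patients respond.
- *Crossing a boundary only pauses the study, and there is other oversight.* Section 13.2 provides monthly reports to the study team and six-monthly DSMB safety reports, section 12.2 requires SAE reports within 24 hours, and section 7.4 has patient-level rules. All true, but none is a numerical study-level trigger, and none says which sentence of section 11.3.5 governs.

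**Conclusion.** The concern holds. As written, the rule and the list cannot both be right. Against the stated rule the list is one DLT too lenient at 9 of 18 sample sizes and never too strict. It stops at 25, short of the 26 evaluable patients targeted and the 30 allowed. The boundaries need no assumption beyond the stated prior, threshold and cut-off. The review probabilities assume a look after each patient, with each DLT outcome known at that look. Because this is the only quantitative study-level safety trigger, it must be corrected, even though the error is never more than one event and a crossing leads to review rather than closure.

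**What to change.** Reconcile the two sentences of section 11.3.5 and carry the list to patient 30.

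- If the stated rule is intended, the counts that follow from it are 3 or more of the first 8-10, 4 of 11-14, 5 of 15-19, 6 of 20-23, 7 of 24-27 and 8 of 28-30.
- If the printed counts are intended, state the prior and cut-off that produce them and use those to derive the entries for 26-30.

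In either case, say which governs, the posterior probability or the table, and give the chance of a review at a few true DLT rates.

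The cost is one sentence. If the counts are brought into line with the stated rule, the chance of a review at a true DLT rate of 10% rises from 5.7% to about 9.5% over 30 patients.
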